4.2.2 Management of Adverse Events

In case of emergency surgery or if patient develops a serious infection, opportunistic or mycobacterium tuberculosis infections treatment of the infection should be initiated promptly according to local standard of care, during the treatment period, treatment with BI 655064 and SOC will be temporarily interrupted and to be restarted once the patient has recovered as per the investigator's judgement. In addition, patients who develop recurrent infections should have their serum IgM and IgG measured according to investigator's assessment.

In case patient develops a thrombosis suspected to be related to immunosuppression during the treatment period, treatment with BI 655064 and SOC will be temporarily interrupted and anti-thrombotic therapy will be started. Treatment with BI 655064 and/or SOC may be restarted once the patient has recovered according to investigator's assessment.

In case of suspected hepatic injury (as defined in [section 5.2.5.1](#)) during the treatment period, treatment with BI 655064 has to be stopped. If the follow-up identifies a confounder (e.g. high dose of paracetamol) and the liver function has recovered, treatment with BI 655064 may be restarted according to the investigator's assessment after discussion with the sponsor.

In case of severe injection reactions, anaphylactic reactions, cytokine release syndrome, or occurrence of lymphoproliferative diseases, treatment with BI 655064 and SOC will be permanently discontinued and must not be re-introduced.

For side effects known to be related to higher doses of MMF or AZA, dose reduction of MMF or AZA should be considered and handled as per the investigator's judgement.

Malignancies

In case of occurrence of malignant neoplasm other than appropriately treated basal cell carcinoma or squamous cell carcinoma of the skin or in situ carcinoma of uterine cervix, the investigator should discontinue treatment with BI655064. Diagnostics and treatment have to be initiated according to local standard of care.

-in case a patient develops neutropenia (< 1000 cells/ μ l) confirmed by a second measurement consider to reduce or suspend MMF, in case the neutropenia worsens

- In case of emergency surgery during treatment in the study, treatment with BI 655064 and MMF (respectively azathioprine) will be interrupted. Treatment with BI 655064 and SOC will be restarted when the patient has recovered according to investigator's assessment.

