A cytokine release syndrome manifests when a large number of immune cells becomes activated and releases inflammatory cytokines. It is consistently associated with elevated TNF α , IFN γ , and IL-6 levels. The cytokine-release syndrome is clinically characterised by fever, chills, rigor and rash. Other symptoms are nausea, dyspnoea, tachycardia and hypotension. Potentially life-threatening complications of a cytokine release syndrome include cardiac dysfunction, respiratory distress syndrome, neurologic toxicity, renal and/or hepatic failure, and disseminated intravascular coagulation. In case of suspicion of a cytokine release syndrome, it is recommended to measure IL-6 levels in the local laboratory if the assay is available.

In general therapy with BI 655064 is immunosuppressive and potentially could increase the risk for infections or lymphoproliferative diseases.

➤ Opportunistic infections and/or severe infections

Opportunistic infections include pneumocystis pneumonia, toxoplasmosis gondii encephalitis, cryptosporidiosis; microsporidiosis, mycobacterium tuberculosis, mycobacterium avium; bacterial respiratory disease, bacterial enteric infection, mucocutaneous candidiasis, invasive mycoses, CMV, EBV, herpes simplex (invasive only), varicella zoster, human herpesvirus 8, JC virus infection.

Any severe infection should also be reported as AESI.

Whenever a patient comes to a visit and reports of an (S)AE related to infections which occurred in the interval since the last visit, then he/she is routinely asked whether they have been seen/treated by a physician and whether blood samples had been taken in that context. Should this be answered in the affirmative then efforts should be undertaken to collect the respective information.

➤ Lymphoproliferative disorders (e.g. B- and T-cell lymphoma, Non-Hodgkin lymphoma and Hodgkin lymphoma, hepatosplenic T-cell lymphoma)

In case of adenopathy, hepato- or splenomegaly, fever of unclear origin, night sweats or loss of weight, occurrence of lymphoproliferative diseases should be evaluated. As the

occurrence of lymphoproliferative disorders is associated with active EBV-infection, patients suffering from active EBV infection should be carefully evaluated for the occurrence of lymphoproliferative diseases.

➤ **Thrombosis and adjunct immunosuppression**

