4. CHANGES IN THE PLANNED ANALYSIS OF THE STUDY

With Amendment #2 to the CTP (21-Dec-2020), Group 2 was cancelled. Group 2 was to be a cohort of patients who achieved a meaningful response to induction treatment outside of 1293.10. With all patients in 1293.13 now coming from trial 1293.10 (Group 1), the sole focus in 1293.13 can be long-term (now 2-year) assessment of their induction and continued maintenance therapy in 1293.13. Efficacy and safety tables and figures will include data from 1293.10 for assessment of BI655064 doses versus placebo over this 2-year treatment period.

Amendment #2 describes the unblinding of treatment codes for 29 patients (20 on treatment and 9 in follow-up) in the trial on 20-Oct-2020. At that time, the investigator was asked to discuss with the patient their treatment options and continued participation in 1293.13. It is not expected that this partial unblinding introduced meaningful reporting bias. The primary endpoint and most of the secondary endpoints are derived from laboratory measurements. With respect to the SLEDAI, most domains are lab-based and other domains are examination findings. No analyses to address potential bias are planned.

The CTP list of secondary and further endpoints was reviewed (prior to release of treatment codes) resulting in some additions and a few deletions essentially driven by learnings from the 1293.10 trial. [Section 5.2](#) lists the secondary endpoints noting the addition of one endpoint (proportion of patients with partial renal response (PRR) without renal flare) inadvertently left off the CTP list of secondary endpoints (but specified in another section) and one deletion with explanation for the deletion (proportion of patients with CRR at Week 52). [REDACTED]

Important Protocol Deviations (iPDs) were updated during trial conduct to reflect learnings and input from Key Opinion Leaders (KOLs). The Per protocol set (PPS) was dropped with the second CTP amendment.

Sensitivity, subgroup and exploratory analyses added to the TSAP for the primary endpoint are listed in [Sections 7.4.2](#). Sensitivity, subgroup and exploratory analyses were also added to the TSAP for an important secondary endpoint; these are listed in [Sections 7.5.2](#).

The biomarker analysis will be outlined outside of this TSAP.

[REDACTED]

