6. GENERAL ANALYSIS DEFINITIONS

6.1 TREATMENTS

For reporting purposes, all patients will be classified into one of the following treatment groups as determined by random treatment assignment at the start of 1293.10:

Sort order	Treatment	Long label	Short label
01	B	BI 655064 120mg	BI 120mg
02	C	BI 655064 180mg	BI 180mg
03	D	BI 655064 240mg	BI 240mg
04	A	Placebo	Placebo

These will be the default labels and sort order for reporting the treatment groups.

The following study periods based on actual start and stop dates of study treatment administration are defined:

Treatment: start date of randomised to double-blind medication in 1293.10 to date of last dose in 1293.13

Follow-up: day after the last dose of randomised double-blind medication in 1293.13 through trial completion and after trial completion

Rules for assigning AEs/laboratory data to the study periods are as follows.

AEs/laboratory data will be assigned to the treatment period if they occur/samples were taken after the first injection of study medication to the date of last administration of study medication plus 50 days.

Adverse events with onset on or after the 51st day after the last administration of trial medication will be considered 'Follow-up' events.

Laboratory data on or after the 51st day after the last administration of trial medication will be considered 'Follow-up' data.

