7.7 EXTENT OF EXPOSURE

Duration of time on treatment starting with the first injection in 1293.10 to the last injection in 1293.13 will be derived for each patient & summarized by treatment group.

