7.8.1 Adverse events

AEs will be analysed using BI standards, as described in the guideline, ‘Handling and summarization of adverse event data for clinical trial reports and integrated summaries’ (4).

Unless otherwise specified, the analyses of adverse events will be descriptive in nature. All analyses of AEs will be based on the number of patients with AEs and NOT on the number of AEs.

The analysis of AEs will be based on the concept of treatment emergent AEs. This means that all AEs occurring between first drug intake and end of the residual effect period (REP) will be assigned to the randomised treatment. The residual effect period is defined as 50 days. All AEs occurring before first drug intake will be assigned to ‘Screening’ and all AEs occurring after last drug intake + 50 days will be assigned to ‘Follow-up’ (and presented in listings only). For details on the treatment definition, see [Section 6.1](#)

According to ICH E3 (5), in addition to Deaths and Serious Adverse Events, ‘other significant’ AEs need to be listed in the clinical trial report. These will be any non-serious adverse event that led to an action taken with study drug (e.g. discontinuation or dose reduced or interrupted).

Proprietary confidential information © 2021 Boehringer Ingelheim International GmbH or one or more of its affiliated companies

An overall summary of adverse events will be presented. The frequency of patients with adverse events will be summarised by treatment, primary system organ class and preferred term. Separate tables will be provided for patients with adverse events leading to treatment discontinuation, other significant adverse events according to ICH E3 (5), related adverse events and serious adverse events. AEs will also be summarised by maximum RCTC grade.

Adverse events of special interest (AESI) will be presented in tables and listings for the following:

- Injection site reactions and hypersensitivity, including anaphylaxis reaction
- Malignancies, lymphoproliferative disorders
- Severe infections and opportunistic infections
- Thromboembolism (Thrombosis and adjunct immunosuppression)
- Cytokine release syndrome
- Drug induced liver injury (DILI) (if applicable)

The system organ classes will be sorted by frequency, PTs will be sorted by frequency (within SOC).

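### Adverse event tables count each patient once over up to about 2.1 years with no adjustment for time at risk, so exposure differences can distort them and recurrent infections cannot show

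*SAP*

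**What the plan says.** SAP 7.8.1 sets the counting unit for all adverse event analyses: "All analyses of AEs will be based on the number of patients with AEs and NOT on the number of AEs". The main display follows from it: "The frequency of patients with adverse events will be summarised by treatment, primary system organ class and preferred term". There are also patient-count tables for serious, related, discontinuation and other significant events, a summary by maximum toxicity grade, and tables and listings for the events of special interest.

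The period is long. SAP section 4 says: "Efficacy and safety tables and figures will include data from 1293.10 for assessment of BI655064 doses versus placebo over this 2-year treatment period". SAP 6.1 defines the period as "Treatment: start date of randomised to double-blind medication in 1293.10 to date of last dose in 1293.13", and SAP 7.8.1 extends it for adverse events: "The residual effect period is defined as 50 days". Later events are listed but not tabulated.

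Exposure is handled separately in SAP 7.7: "Duration of time on treatment starting with the first injection in 1293.10 to the last injection in 1293.13 will be derived". It is summarised by arm, and nothing visible in SAP 7.8 uses it as a denominator.

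On infection, Protocol 5.2.5.1 says: "In general therapy with BI 655064 is immunosuppressive and potentially could increase the risk for infections or lymphoproliferative diseases". Protocol 4.2.2 foresees repeat episodes: "patients who develop recurrent infections should have their serum IgM and IgG measured".

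**The concern.** A percentage of patients with at least one event compares arms fairly only if patients are observed for about the same time. Here they may not be. SAP 6.6.1 refers to unblinded placebo patients who stopped injections with the sponsor's approval, and under SAP 6.1 their on-treatment window closes 50 days after the last injection. A shorter placebo window lowers the placebo percentages and can make the active arms look worse with no true difference.

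The second problem works the other way. If an event is common, many patients in every arm have it at least once in two years, and the percentages draw together. A patient with one infection and a patient with six count the same, so a true excess can look small. The planned tables give the reader no means of separating the two effects, and none shows recurrence, which the protocol itself anticipates.

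**Working it through.** The plan states no adverse event rate and no power figure, so there is nothing to reproduce. All rates below are assumptions.

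**Window length.** Two 52-week treatment periods plus 50 days: 2 × 364 + 50 = 778 days, and 778 / 365.25 = 2.13 years. A patient stopping 26 weeks early has 778 − 182 = 596 days, or 1.63 years. A patient stopping straight after roll-over has 364 + 50 = 414 days, or 1.13 years. The longest and shortest differ by a factor of 778 / 414 = 1.88.

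**Unequal time, equal rates.** With a constant rate λ, the chance of at least one event in time t is 1 − exp(−λt). At λ = 0.5 per year:

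- completer: 1 − exp(−0.5 × 2.13) = 65.5%
- stopping 26 weeks early: 1 − exp(−0.5 × 1.63) = 55.8%

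The gap is 9.7 points from exposure alone. With gamma frailty of shape 2 it is 57.4% against 49.6%, about 8 points. At λ = 0.1 without frailty it is 19.2% against 15.1%, so rare events are affected too. These are per-patient figures. If a fraction f of the placebo arm stopped 26 weeks early, the arm-level gap at λ = 0.5 is 9.7 × f points, for example 3.2 points for one third. The documents do not give f or the stopping times.

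**Compression of a true difference.** Take two years and a true rate ratio of 1.5. Let patients differ in susceptibility (gamma frailty, shape 2). The chance of at least one event is then 1 − (1 + λt/2)^(−2), which at t = 2 is 1 − (1 + λ)^(−2).

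| Placebo rate per year | Active rate per year | Placebo, % with ≥1 | Active, % with ≥1 | Ratio of percentages |
|---|---|---|---|---|
| 0.5 | 0.75 | 1 − 1.5^(−2) = 56 | 1 − 1.75^(−2) = 67 | 1.21 |
| 1.0 | 1.5 | 1 − 2^(−2) = 75 | 1 − 2.5^(−2) = 84 | 1.12 |
| 1.5 | 2.25 | 1 − 2.5^(−2) = 84 | 1 − 3.25^(−2) = 91 | 1.08 |

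An event rate per patient-year targets 1.5 in each row. At a rare 0.1 per year (same frailty, 2.13 years) the percentages are 18.3 against 25.7, a ratio of 1.40, so little is lost.

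**The case against.** Patient-level incidence is a standard summary, the SAP chose it openly, and safety is descriptive with no test planned (Protocol 7.3.4). All of that is true. The additions proposed here are descriptive as well and replace nothing.

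SAP 7.8.1 defers to a sponsor guideline that is not available, and some SAP text is missing. The quoted rule does not itself forbid adjusting for time: patients with an event per patient-year would comply with it. The time-at-risk point therefore rests on the absence of any such rate from the visible text. The exclusion of event counts is explicit.

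Several stronger readings are tempting, and the documents do not support them.

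- A reader might infer that infection is the drug's main expected harm. Protocol 5.2.5.1 calls it a potential risk, names it beside lymphoproliferative disease and ranks neither.
- A reader might infer that most patients in every arm will have an infection, so that the tables are bound to saturate. No infection rate is given. Without frailty the highest assumed rate gives 95% against 99%, but allowing for patients who differ in susceptibility gives 84% against 91%.
- A reader might infer that an excess could not appear in any planned table. The serious, special-interest, discontinuation, other-significant and maximum-grade tables could each show part of it, and the listings let recurrences be counted by hand. They give no comparison of recurrence by arm.
- A reader might judge the loss by the power of a test of all active doses pooled against placebo. No such safety contrast is planned.

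What stands is that arms are small. About 60 patients are expected over four unbalanced arms, so any rate will be imprecise.

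**Conclusion.** The point holds as a gap in the safety presentation that is cheap to close. It is not an error in a stated figure.

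Unequal time at risk is the firmer part, because the SAP itself shows that some placebo patients stopped early. Its size is about 10 points for a patient stopping 26 weeks early at an assumed 0.5 events per year, scaled down by the unknown fraction who did so. Compression is real for common events: a rate ratio of 1.5 shows as 1.21 to 1.08 at assumed placebo rates of 0.5 to 1.5 per year. It is small for rare preferred terms and probably for the severe or opportunistic infection category. The two effects pull in opposite directions, so the direction of any net distortion cannot be stated in advance.

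**What to change.** Keep every planned patient-count table. Amend SAP 7.8.1 to add, descriptively and by randomised arm:

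- For the Infections and infestations system organ class: the number of events, patient-years at risk (treatment time plus the 50-day residual effect period), events per 100 patient-years with an interval that allows for overdispersion, and the number of patients with 0, 1, 2 and 3 or more infections.
- For all adverse events, serious adverse events and each event of special interest: patients with a first event per 100 patient-years, with time at risk ending at the first event or the end of the window.

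Reword the sentence that excludes event counts so that it allows the first item. State that events carried over from 1293.10 and re-entered at Visit 1 (Flow Chart 1, footnote 16) are de-duplicated before counting. No hypothesis test is needed.

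The cost is a few lines of text and two or three tables from adverse event and dosing data that the trial already collects. Intervals will be wide. With an assumed 15 patients in an arm (60 / 4), 1.0 infection per year, 2.13 years and frailty of shape 2, the standard error of the log rate is √[(1/2.13 + 0.5)/15] = 0.25, so a 95% interval runs from about 0.6 to 1.6 times the estimate. The report should say so.

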7.3.4 Safety analyses

Adverse events will be coded using the Medical Dictionary for Drug Regulatory Activities (MedDRA). Standard BI summary tables and listings will be produced. All adverse events with an onset between start of treatment and end of the residual effect period (REP), a period of 50 days after the last dose of trial medication, will be assigned to the on-treatment period for evaluation. Analysis will be performed based on randomised treatment.

All treated patients will be included in the safety analysis. In general, safety analyses will be descriptive in nature and based on BI standards. No hypothesis testing is planned. Statistical analysis and reporting of adverse events will concentrate on treatment-emergent adverse events, i.e. all adverse events occurring between start of treatment and end of the REP. Adverse events that start before first drug intake and deteriorate under treatment will also be considered as 'treatment-emergent'.

Frequency, severity and causal relationship of adverse events will be tabulated by system organ class and preferred term after coding according to the current version of the MedDRA at the database lock.

AESIs will be summarized separately using a standard BI summary table. Note that there is one SAE definition specified in [Section 5.2.5.1](#) for Japan only. Laboratory data will be analysed both quantitatively as well as qualitatively. The latter will be done via comparison of laboratory data to their reference ranges. Values outside the reference range as well as values defined as clinically relevant will be summarised. Treatment groups will be compared descriptively with regard to distribution parameters as well as with regard to frequency and percentage of patients with abnormal values or clinically relevant abnormal values.

Vital signs, physical examinations, or other safety-relevant data observed at screening, baseline, during the course of the trial and at the end-of-trial evaluation will be assessed with regard to possible changes compared to findings before start of treatment.

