3. INTRODUCTION

The purpose of this document is to provide a more technical and detailed elaboration of the principal features of the analysis than was described in the protocol, and to include detailed procedures for executing the statistical analysis of the primary and secondary endpoints and other data.

This TSAP assumes familiarity with the Clinical Trial Protocol (CTP), including Protocol Amendments. In particular, the TSAP is based on the planned analysis specification as written in CTP Section 7 “Statistical Methods and Determination of Sample Size”. Therefore, TSAP readers may consult the CTP for more background information on the study, e.g., on study objectives, study design and population, treatments, definition of measurements and variables, planning of sample size, randomization.

SAS[®] Version 9.4 (or later version) will be used for all analyses.

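### The SAP drops, without declaring it, the protocol's rule that AEs starting before first drug intake and deteriorating on treatment are treatment-emergent

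*SAP*

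**What the plan says.** Protocol 7.3.4 builds the treatment-emergent definition in two parts. The first is the time window: "all adverse events occurring between start of treatment and end of the REP", where the residual effect period (REP) is 50 days after the last dose. The second extends it: "Adverse events that start before first drug intake and deteriorate under treatment will also be considered as" treatment-emergent.

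SAP 7.8.1 carries over only the first part: "all AEs occurring between first drug intake and end of the residual effect period (REP) will be assigned to the randomised treatment". Its next rule covers earlier events: "All AEs occurring before first drug intake will be assigned to" Screening. No exception is made for events that worsen.

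SAP 6.1 is consistent with that: "AEs/laboratory data will be assigned to the treatment period if they occur/samples were taken after the first injection of study medication", with the upper limit at last administration plus 50 days. It also fixes when treatment begins, running the treatment period from "start date of randomised to double-blind medication in 1293.10 to date of last dose in 1293.13".

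SAP section 3 states that "the TSAP is based on the planned analysis specification as written in CTP Section 7", which is the protocol section containing the deterioration clause. SAP section 4, which sets out changes to the planned analysis, does not mention the clause.

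**The concern.** The two current documents sort the same event differently. The deterioration clause still stands in protocol version 3.0, although Amendment 2 revised section 7.3.4. SAP version 2 (17 June 2021) post-dates that amendment (21 December 2020). So this is a difference between two texts in force, and it is either an oversight or a change that was not declared.

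At stake is which events the main safety tables count. SAP 7.8.1 bases its AE analysis on treatment-emergent events, with tables for AEs overall, serious AEs, related AEs, AEs leading to discontinuation, AEs of special interest and maximum RCTC grade. Protocol 5.2.5.1 describes the product as immunosuppressive, with a potential to raise infection risk. An infection present before dosing that becomes severe on drug is the sort of event a deterioration clause is meant to keep in view.

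**Working it through.** There is no stated figure to reproduce, so the check compares the texts and applies each rule to one event.

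**1. The rules side by side**

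| Element | Protocol 7.3.4 | SAP 6.1 and 7.8.1 |
|---|---|---|
| AE from first intake to end of REP | Treatment-emergent | Treatment-emergent |
| REP | 50 days | 50 days ("The residual effect period is defined as 50 days") |
| AE starts before first intake, does not worsen | Not treatment-emergent | Screening |
| AE starts before first intake, deteriorates on treatment | Treatment-emergent | Screening |
| Declared in SAP section 4 | n/a | No |

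Only the fourth row differs. SAP 6.1 also defines just two periods, Treatment and Follow-up, so the Screening category used in 7.8.1 has no definition there.

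**2. Does the SAP's word for occurring mean onset?** The SAP uses the term onset only for follow-up events. Reading it as onset elsewhere is an inference, but a well-supported one. Protocol 7.3.4 uses onset and occurring for the same window. If occurring also covered continuing, an AE that started before dosing and was still present afterwards would fall in both Screening and Treatment, and the rule could not assign it.

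**3. A test event.** Suppose an AE starts at grade 1 before the first injection and reaches grade 3 on treatment, kept under one record with its original onset date. Under protocol 7.3.4 it is treatment-emergent. Under SAP 6.1 and 7.8.1 it is Screening and outside the treatment-emergent tables.

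**4. Which events are left in the gap?**
- The SAP window opens at the first 1293.10 dose. AEs ongoing at roll-over, which Flow Chart 1 (footnote 16) requires to be re-entered at Visit 1, are already on-treatment if they began after that dose. Only AEs that began before it remain.
- Protocol 5.2.5.2 asks for worsening of pre-existing conditions to be recorded as an AE, and protocol 5.2.1 does the same for worsening found at physical examination. If the site opens a new record, its onset is on treatment and it is counted. Only worsening held under the original record is lost.
- SAP 7.8.1 counts patients, not events. A patient leaves a given table only if no other qualifying AE puts them in it.

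**5. Scale, as illustration only.** The documents give no number of pre-dose AEs. Assume that 10% to 20% of the approximately 60 patients had an AE before the first dose and that 10% to 25% of those worsened on treatment:
- low: 60 × 0.10 × 0.10 = 0.6 patients
- high: 60 × 0.20 × 0.25 = 3.0 patients

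Both percentages are assumptions, and both results precede the last two limits in step 4. An equal split over four arms gives 60 / 4 = 15, and one patient is 1 / 15 = 6.7 percentage points. The equal split is also an assumption: SAP 7.4.1 says the groups are not balanced.

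**The case against.** The strongest reply is that the SAP does not stand alone. SAP 7.8.1 says AEs are analysed to sponsor standards under a cited guideline, and that guideline may carry a rule for worsened events. Its content is not in the documents, so this can be neither confirmed nor excluded. It does mean that the loss of these events is the literal reading of the SAP and not an established outcome. It does not remove the point, because the SAP's explicit text makes no exception and a reader cannot tell which source prevails.

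The second reply is that the recording rules already catch worsening. This stands where a site enters a new AE. It does not settle the case of an AE already recorded before dosing: AEs are collected from consent onward, the documents do not say how worsening of such an AE is dated, and the protocol kept its deterioration clause alongside those recording rules.

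Third, some worsening would be visible elsewhere. SAP 7.8.2 provides laboratory abnormality criteria using RCTC and plots of white cells and neutrophils, so a worsening cytopenia does not depend on AE onset to be seen. That stands for laboratory events. It does not help for a clinical event such as an infection.

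A reader might infer that the SAP removes affected patients from every safety table, or that it favours the active arms. The documents support neither. A patient with another qualifying AE stays in the table, and the rule applies to placebo in the same way as to active treatment, so no direction between arms follows.

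**Conclusion.** The inconsistency is real, current and undeclared. It is minor. On the SAP's literal wording, an event is missed only if it began before the first 1293.10 dose, worsened on treatment and stayed under its original record. It changes a table only if that patient has no other qualifying AE there. The number is unknown and probably small. Where a category is rare, such as a serious AE or a severe infection, a single event could separate none from one, but nothing in the documents shows that this happens.

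A reader might go further and conclude that harm is understated. That would need counts of pre-dose AEs, knowledge of how worsening was recorded, and the content of the sponsor guideline, none of which the documents provide. The conclusion rests on reading the SAP's term occurring as onset, and on the guideline not overriding the SAP text.

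**What to change.** Restore the protocol clause in SAP 6.1 and 7.8.1, for example: AEs that start before first drug intake in 1293.10 and deteriorate between first intake and last dose plus 50 days are assigned to the randomised treatment as treatment-emergent; the remaining pre-dose AEs are assigned to Screening.

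Base deterioration on the worsening data actually collected. The clause should go no further than the protocol: 7.3.4 sets no grade or seriousness threshold, does not move the onset date to the date of worsening, and does not treat an event as treatment-emergent by default when no worsening date exists. If the clause was dropped on purpose, SAP section 4 should say so and give the reason.

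The cost is one derivation flag and a small edit in two sections. AE rates may become slightly less favourable. No trial procedure changes.
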